2. Received and completed primary mRNA COVID-19 vaccine under EUA dosing guidelines and one or two doses of Ad26.COVS.2 at least 12 weeks prior to enrollment (Cohort 1 only).
3. Willing and able to comply with all scheduled visits, vaccination plan, laboratory tests and other study procedures.
4. Determined by medical history, targeted physical examination and clinical judgement of the investigator to be in good health.

Note: Healthy volunteers with pre-existing stable disease, defined as disease not requiring significant change in therapy or hospitalization for worsening disease during the 6 weeks before enrollment, can be included.

5. Female participants of childbearing potential may be enrolled in the study, if all of the following apply:
 - Practiced adequate contraception for 28 days prior to the first dose of vaccine (Day 1),
 - Has agreed to continue adequate contraception through 3 months following the booster dose,
 - Has a negative pregnancy test at screening and on the day of the first study vaccine dose (Day 1),

- Is not currently breastfeeding.

Exclusion Criteria:

Participants meeting any of the following criteria will be excluded from the study:

1. Known history of SARS-CoV-2 infection (for Cohort 1 and the primary series of Cohort 2).
2. Prior administration of an investigational coronavirus (SARS-CoV, MERS-CoV) vaccine or SARS-CoV-2 monoclonal antibody in the preceding 90 days or current/planned simultaneous participation in another interventional study.
3. Receipt of SARS CoV-2 vaccine prior to study entry (Cohort 2 only).
4. A history of anaphylaxis, urticaria, or other significant adverse reaction requiring medical intervention after receipt of a vaccine or nanolipid particles.
5. Receipt of any investigational study product within 28 days prior to enrollment.
6. Received or plans to receive a vaccine within 28 days prior to the first dose (Day 1) or plans to receive a non-study vaccine within 28 days prior to or after any dose of study vaccine (with exception for seasonal influenza vaccine within 14 days of study vaccine).
7. Bleeding disorder diagnosed by a doctor (e.g., factor deficiency, coagulopathy, or platelet disorder requiring special precautions) or significant bruising or bleeding difficulties with intramuscular injections or blood draws, or previously experienced thrombosis with thrombocytopenia (TTS) or heparin-induced thrombocytopenia.

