- 8E - Evaluates mRNA-1273 EUA vaccination series followed by a homologous platform delayed dose of BNT162b2
- 9E - Evaluates BNT162b2 EUA vaccination series followed by a homologous platform delayed dose of BNT162b2
- 10E- Evaluates Ad26.COVS2.S EUA vaccination series followed by a heterologous platform delayed dose of a combined homologous and variant spike lineage mRNA-1273.211
- 11E - Evaluates BNT162b2 EUA vaccination series followed by a homologous platform delayed dose of a combined homologous and variant spike lineage mRNA-1273.211
 - Note – the homologous comparator for groups 10E and 11E (Moderna EUA vaccination with the mRNA 1273.211 homologous and variant vaccine is being conducted in another trial (NIAID DMID 21-0002) and not done here to avoid duplication.
- 12E – Evaluates a heterologous platform 50 mcg booster of mRNA-1273 among persons who previously received an Ad26.COVS2.S EUA vaccination series
- 13E- Evaluates a homologous platform 50 mcg booster of mRNA-1273 among persons who previously received a mRNA-1273 EUA vaccination series
- 14E – Evaluates a homologous mRNA platform of mRNA-1273 50 mcg booster among persons who previously received a BNT162b2 EUA vaccination series
- 15E - Evaluates Ad26.COVS2.S EUA vaccination series (one or two doses)* followed by a heterologous platform delayed dose of NVX-CoV2373 (5 mcg SARS-COV-2)
- 16E - Evaluates mRNA-1273 EUA vaccination series followed by a heterologous platform delayed dose of NVX-CoV2373 (5 mcg SARS-COV-2)
- 17E - Evaluates BNT162b2 EUA vaccination series followed by a heterologous platform delayed dose of NVX-CoV2373 (5 mcg SARS-COV-2)

*Since the regimen of one or two doses of Ad26.COVS2.S is less prevalent than other EUA dosing regimens, it will make this group harder to recruit. Therefore, Group 4E participants who have received two doses of Ad26.COVS2.S will be offered the opportunity to roll into Group 15E. Newly recruited volunteers who have received a single dose of Ad26.COVS2.S will also be recruited. Subset analysis will be performed on the one and the two dose arms. Data is needed as to the best means of boosting this under-evaluated regimen.

Cohort 2 will include approximately 250 participants per group aged ≥ 18 years of age who have not received a COVID-19 vaccine and have no known history of COVID-19 or SARS-CoV-2

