*Note - Groups 15E-17E is planned to include 60 participants, split (approximately evenly) between age strata as able. As the use of 2 doses of Ad26COV2.S without additional vaccines is relatively infrequent in the population (and 1 dose without additional vaccines is even less frequent), participants who are enrolled and remain active in Group 4E (homologous prime-boost with Ad26COV2.S) are offered the opportunity to roll into Group 15E, if eligible. Data collected on these participants after their enrollment in Group 15E will not be included in Group 4E analyses.

Participants in Cohort 1 receive a single IM injection of the designated delayed booster vaccine and are followed through 12 months after vaccination. A telephone visit is performed at Day 8 and in-person follow-up visits occur on Days 15 and 29, as well as 3, 6, 9, and 12 months after the vaccination.

Cohort 2 is planned to include approximately 250 participants per group aged > 18 years of age who have not received a COVID-19 vaccine and have no known history of COVID-19 or SARS-CoV-2 infection. Participants are assigned to receive COVID-19 vaccine under EUA dosing as programmatically outlined in Table 9 of the protocol. Additional pools of participants are included as needed as additional COVID-19 vaccines are awarded EUA. These pools of participants are assigned a novel homologous or heterologous variant boost or heterologous platform boost at a minimum of 12 weeks following receipt of EUA dosing and followed through 12 months after the last vaccination. All Cohort 2 volunteers are offered a booster of mRNA-1273 at the approved 50 mcg dose at Day 181 (+/- 30 days) following dose 2 of their primary series. A telephone visit is performed one week after each primary EUA vaccination and one week after the booster

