6.3.1. Safety Population

The Safety Population includes all participants who received at least one dose of the delayed Janssen-Ad26.COV2.S booster vaccine.

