9. SAFETY EVALUATION

Summaries and analysis of safety data will be presented for the Safety Population. Safety summaries will be presented overall and grouped by study group.

Solicited AEs will be summarized by severity for each day post vaccination (Days 1-8) and as the maximum severity over all 8 days. Solicited AEs that were ongoing beyond Day 8 will be summarized in the Day 8+ and maximum post baseline columns. Additionally, solicited AEs will be analyzed by taking the most severe response over the follow-up period and using standard techniques, such as exact confidence intervals (CI), to summarize the proportion of participants reporting each symptom, any local symptom, and any systemic symptom.

Unsolicited non-serious AEs will be collected from the time of the delayed boost vaccination through 28 days after vaccination. Unsolicited AEs will be coded by MedDRA for preferred term and system organ class (SOC). SAEs, protocol specified AESIs, MAAEs, and NOCMCs will be collected from the time of delayed boost vaccination through the end of planned study participation. The information collected on SAEs, AESIs, NOCMCs, and MAAEs will be reported in detailed listings showing the event description, MedDRA preferred term and SOC, relevant dates (study boost vaccination and onset/resolution of AEs), severity, relatedness, and outcome for each event. Non-serious unsolicited AEs will be summarized as number and percentage of participants reporting at least one event in each MedDRA preferred term and SOC, cross tabulated by severity and relationship to study vaccination. Additionally, the proportion of participants and exact 95% CIs of AEs in aggregate and by MedDRA categories will be computed.

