9.3. Adverse Events

When calculating the incidence of adverse events (i.e., on a per participant basis), each participant will only be counted once and any repetitions of adverse events within a participant will be ignored; the denominator will be the total population size. All adverse events reported will be included in the summaries and analyses. A summary of all adverse events is provided in Table 50. A summary of those events that occurred in $\geq 5\%$ of participants in any study group is provided in Table 51. Frequency of adverse events will be defined as the total number of adverse events including all repetitions of adverse events within a participant.

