9.4. Deaths, Serious Adverse Events and other Significant Adverse Events

SAEs will be summarized by MedDRA SOC and PT (Table 59). The following listings will be presented including Participant ID, Adverse Event Description, Adverse Event Onset Date/Days Post Dose, Severity, Reason Reported as an SAE, Relationship to Study Vaccination, Alternate Etiology if not Related, Outcome, and Duration of Event (days), MedDRA SOC and PT:

- Deaths and Serious Adverse Events (Table 60);
- Protocol specified Adverse Events of Special Interest (AESIs); New Onset Chronic Medical Conditions (NOCMCs); Medically Attended Adverse Events (MAAEs) (Table 62)

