14.3 Safety Data

14.3.1 Displays of Adverse Events

Table 50:Overall Summary of Adverse Events

	[Dosec Boost	oup 4E l Janssen, Janssen] N=X)	[Dosed Boost	oup 5E Moderna, Janssen] N=X)	[Dose Boost	oup 6E d Pfizer, Janssen] N=X)		rticipants = xx)
Participants ^a with	n	%	n	%	n	%	n	%
At least one local solicited adverse event	x	x	x	x	x	x	x	x
At least one systemic solicited adverse event	x	x	x	x	x	x	x	x
At least one unsolicited adverse event	x	x	x	X	x	x	X	x
At least one related unsolicited adverse event	x	x	x	x	x	x	x	x
Mild (Grade 1)	x	х	х	x	х	x	х	х
Moderate (Grade 2)	x	х	х	x	х	x	x	x
Severe (Grade 3)	x	x	x	x	x	x	x	x
At least one severe (Grade 3) unsolicited adverse event	x	x	x	x	x	x	x	x
Related	x	х	х	х	х	x	x	X
Unrelated	x	x	X	x	X	x	X	X
At least one serious adverse event ^b	x	x	x	x	x	x	x	x
At least one related, serious adverse event	x	x	x	x	X	x	X	x
At least one medically attended adverse event	x	x	x	x	x	x	x	x
At least one new onset chronic medical condition	х	х	х	x	x	x	x	х
At least one adverse event of special interest N = Number of participants in the Safety Population ^a Participants are counted once for each category regardles	s of the pu	mber of ever	nts					

^a Participants are counted once for each category regardless of the number of events. ^b A listing of Serious Adverse Events is included in Table 57.

Adverse Events Occurring in 5% of Participants in Any Study Group by MedDRA Table 51: System Organ Class and Preferred Term, and Study Group - Safety Population

MedDRA System Organ Class	Preferred Term		osed oost J	1p 4E Janssen, [anssen] =X)		osed I Soost J	ıp 5E Moderna, [anssen] =X)	-	Dosed oost J	up 6E l Pfizer, [anssen] =X)	Al		ticipants =X)
		n	%	Events	n	%	Events	n	%	Events	n	%	Events
Any Adverse Event ^a													
All	All	x	х	х	x	х	х	x	x	х	x	х	х
Non-serious Adverse Events					•								
All	All	x	х	х	x	х	x	x	x	x	x	х	х
SOC1	PT1	x	х	х	x	х	х	x	x	х	x	х	х
Etc.	Etc.												
Solicited Adverse Events	•					1	L				L		
All	All	x	х	х	x	х	х	x	x	х	x	х	х
SOC1	PT1	x	х	х	x	х	х	x	х	x	x	х	х
Etc.	Etc.												
N = number of participants in the Sa n= number of participants reporting Events= total frequency of events re Solicited events ongoing past Day 8 ^a Includes only non-serious adverse of	event. ported. are included as unsoli	cited	event	ts.		% three	eshold.		1	1		1	 

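### Group 4E data stop at entry to Group 15E, but the end-of-study safety percentages keep every boosted 4E participant in the denominator and report no follow-up time

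*SAP*

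**What the plan says.** The protocol (4.1) explains that people with only Ad26 doses are hard to recruit, so "Group 4E participants who have received two doses of Ad26.COVS2.S will be offered the opportunity to roll into Group 15E". The SAP (4.1) repeats the offer for those still active in 4E and eligible, and adds the cut: "Data collected on these participants after their enrollment in Group 15E will not be included in Group 4E analyses".

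The safety sections carry no matching rule:

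- **Population (SAP 6.3.1).** "The Safety Population includes all participants who received at least one dose of the delayed Janssen-Ad26.COV2.S booster vaccine".
- **Incidence (SAP 9.3).** "the denominator will be the total population size".
- **Window (SAP 9).** "SAEs, protocol specified AESIs, MAAEs, and NOCMCs will be collected from the time of delayed boost vaccination through the end of planned study participation". Planned Cohort 1 follow-up is 12 months.
- **Displays.** Table 50 gives n and % for all four categories, by group and for all participants, with "N = Number of participants in the Safety Population". Table 59 gives serious events by class and term in the format of Table 58 (n, % with exact interval, events).

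SAP 6.5, on missing data and censoring, deals with missing values and assay limits. It has no rule for shortened safety follow-up.

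On disposition, SAP 7.1 and Table 7 have open early-termination reasons, an Other row and a completion row. Neither says where a rollover belongs. Table 49 counts boosts received outside the study and has a residual row for participants without evidence of infection or boost.

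**The concern.** The numerator and denominator of the 4E long-term percentages cover different follow-up. Groups 5E and 6E have no route into 15E, so the shortfall falls on 4E alone and passes into the All Participants column of Table 50. Safety is a co-primary objective, and SAP Table 1 labels 4E the control strategy, so its column will be read beside the other two. The event listings give onset days but not the time each person was observed.

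The reporting gap makes this hard to see. If rollovers are coded as early terminations, they appear in the reason rows of Table 7 and, with study day, in Listing 2. If they are coded as completers, they appear in neither. The 15E dose is a study dose, so Table 49 as labelled does not count it, and a rollover could land in the residual row.

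**Working it through.** **1. Which endpoints can be affected.** Cohort 1 entry requires the last Ad26 dose at least 12 weeks (84 days) earlier (protocol synopsis, inclusion criterion 2). For a 4E participant that dose is the Day 1 study boost, so rollover cannot occur before about Day 85. Solicited events (7 days), unsolicited non-serious events (28 days) and Day 15 and Day 29 titers are complete by then. Later titer tables print n at each visit, so their denominators shrink visibly. That leaves serious events, AESIs, MAAEs and NOCMCs between about Day 85 and Day 366.

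**2. The plan's own figure.** SAP section 5 gives a 99.5% chance of at least one event of probability 10% in 50 people: 1 − 0.9^50 = 0.9948. It reproduces, but it assumes all 50 are observed for the whole window. With an assumed 20 of 50 leaving at Day 181 and constant hazard, it becomes 98.5%. For a 2% event the stated 63.6% becomes 55.3%.

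**3. Expected crude 4E percentage.** Let I be the true 12-month risk, r the fraction rolling over and t the study day of rollover. With constant hazard:

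crude = (1 − r)·I + r·[1 − (1 − I)^((t − 1)/365)]

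None of I, r and t is in the documents; all are assumptions. For I = 10%, a participant cut at Day 181 has risk 1 − 0.9^(180/365) = 5.06%. At Day 273 it is 7.55%, and at Day 340 it is 9.32%.

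| Rollover day | r = 30% | r = 50% | r = 70% |
|---|---|---|---|
| 181 | 8.5% | 7.5% | 6.5% |
| 273 | 9.3% | 8.8% | 8.3% |
| 340 | 9.8% | 9.7% | 9.5% |

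Example: r = 70%, Day 181 gives 0.3 × 10 + 0.7 × 5.06 = 6.5%. Groups 5E and 6E would show 10%. In people, Days 181–273 give 3.3–4.6 expected instead of 5 of 50. With three groups of 50, the All Participants figure would be (6.54 + 10 + 10)/3 = 8.8% to (9.27 + 10 + 10)/3 = 9.8%. Over the same days, 4E shows 3.2–4.6% at a 5% risk and 13.3–18.6% at a 20% risk.

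**4. If events cluster early.** Put a share f of events evenly in the first 42 days and the rest evenly to Day 366 (I = 10%, same r and Days 181–273). With f = 0.5 the crude figure is 8.0–9.6%; with f = 0.8, 9.2–9.8%; with f = 1 there is no loss.

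**5. Against sampling error.** The exact 95% interval for 5/50 is 3.3–21.8%, far wider than any shift above.

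**6. Would censoring at 15E entry repair it?** At constant hazard and with uninformative rollover, yes. But rollover requires eligibility, which includes good health and no known SARS-CoV-2 infection. Suppose rollovers have half the hazard of the others, the group risk is 10%, and 50% roll over at Day 181. Solving 0.5(1 − e^(−h/2)) + 0.5(1 − e^(−h)) = 0.10 gives h = 0.141 per year of follow-up.

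- Crude: 0.5 × 13.18 + 0.5 × 3.42 = 8.3%.
- Kaplan-Meier: survival to rollover is 0.5 × 0.9658 + 0.5 × 0.9327 = 0.9493. Those who stay then survive the rest with probability 0.9309. So 1 − 0.9493 × 0.9309 = 11.6%.

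The two errors are about equal and opposite (−1.7 and +1.6 points).

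**The case against.** The case for leaving the plan alone has four parts.

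- **Size.** No rollover count or date is in the documents, so any figure is assumed. Late or rare rollover makes the shift negligible, and early clustering removes it. MAAEs are vaccine-related by the protocol's definition, and Guillain-Barré syndrome is described as mostly within 42 days, so the loss falls mainly on late background events. This stands, and it limits the claim to an expected direction. A reader might infer that 4E will look materially safer than 5E and 6E; the documents do not support that.
- **No planned comparison.** The trial is non-randomized and tests no hypothesis, and the long-term events are also listed individually. This stands too. It does not remove the mismatch, because the percentages are still printed side by side.
- **The remedy.** A reader might infer that Kaplan-Meier should replace the crude percentage. Step 6 shows why not: with selective rollover it errs upward by about as much.
- **Visibility.** Rollovers may appear in Table 7's open reason rows and Listing 2, and the planned CONSORT figure is not shown in the available text, so its boxes cannot be checked. It would therefore go too far to say that the plan hides them. What stands is that the SAP does not say how they are classed.

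Nor is the cut itself at fault: ending 4E data at the next vaccine is reasonable.

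**Conclusion.** The mismatch follows directly from the SAP's text. Applied as written, with any rollover before Day 366, the plan gives 4E end-of-study percentages that are expected to be too low relative to 5E and 6E at the same event rate. There is no follow-up time from which a reader could see it. Confidence is high in that wording gap and low in any particular size. The illustrative 6.5–9.3% (Day 181–273) and 9.5–9.8% (Day 340), against 10%, rest on assumed risk, rollover fraction, timing and constant hazard. This is a modest reporting correction for one arm's late safety events. It does not threaten the short-term safety or early immunogenicity results.

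**What to change.** 1. Keep crude n/N in Tables 50 and 59. Add total follow-up time (person-time) per group, with 4E follow-up ending at 15E enrollment. A cumulative incidence censored at that date may be added as a supplementary estimate only. Footnote it: rollover requires eligibility and good health, so censoring may be informative, and this estimate may err upward while the crude figure errs downward.
2. State whether a rollover is an early termination or a completion. Show the rollover count and study day in Table 7 and the CONSORT figure.
3. In Table 49, do not count the 15E dose as an outside boost, since that would bring post-cut data into a 4E table. Give rollovers their own row, labelled as follow-up ended at 15E enrollment, so that they do not fall in the residual row.

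The cost is some SAP wording and a few rows and columns. The 15E enrollment date and event onset days are already needed to apply the cut, so no new data are required. The downside is slightly more tabulation, and wide intervals where events are few.

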*Note – Groups 15E-17E will enroll 60 subjects, split (approximately evenly) between age strata as able. As the use of 2 doses of Ad26COV2.S without additional vaccines is relatively infrequent in the population (and 1 dose without additional vaccines is even less frequent), participants who were enrolled and remain active in Group 4E (homologous prime-boost with Ad26COV2.S) will be offered the opportunity to roll into Group 15E, if eligible.

Subjects in Cohort 1 will receive a single intramuscular (IM) injection of the designated delayed booster vaccine and will be followed through 12 months after vaccination. A telephone visit will occur at Day 8 and in-person follow-up visits will occur on Days 15 and 29, as well as 3, 6, 9, and 12 months after the vaccination.

Table 8: Cohort 1 Treatment Arms

Arm	Sample Size	Booster Vaccination Product and Dose
1E	~50	100 mcg mRNA-1273
2E	~50	100 mcg mRNA-1273
3E	~50	100 mcg mRNA-1273
4E	~50	5x10 ¹⁰ vp dose Ad26.COVS2.S
5E	~50	5x10 ¹⁰ vp dose Ad26.COVS2.S
6E	~50	5x10 ¹⁰ vp dose Ad26.COVS2.S
7E	~50	30 mcg BNT162b2
8E	~50	30 mcg BNT162b2
9E	~50	30 mcg BNT162b2
10E	~50	100 mcg mRNA-1273.211
11E	~50	100 mcg mRNA-1273.211
12E	~50	50 mcg mRNA-1273
13E	~50	50 mcg mRNA-1273
14E	~50	50 mcg mRNA-1273
15E	~60	NVX-CoV2373 (5 mcg Prototype SARS-CoV-2 rS with 50 mcg Matrix-M)
16E	~60	NVX-CoV2373 (5 mcg Prototype SARS-CoV-2 rS with 50 mcg Matrix-M)
17E	~60	NVX-CoV2373 (5 mcg Prototype SARS-CoV-2 rS with 50 mcg Matrix-M)

Summary of Treatment Arms:

- 1E – Evaluates a heterologous platform booster dose of mRNA-1273 among persons who previously received an Ad26.COVS2.S EUA vaccination series
- 2E- As a bridging arm evaluates a homologous platform third boosting dose of mRNA-1273 among persons who previously received a mRNA-1273 EUA vaccination series
- 3E – Evaluates a homologous mRNA platform of mRNA-1273 booster dose among persons who previously received a BNT162b2 EUA vaccination series

- 4E - Evaluates Ad26.COVS2.S EUA vaccination series followed by a homologous platform delayed dose of Ad26.COVS2.S*
- 5E - Evaluates mRNA-1273 EUA vaccination series followed by a heterologous platform delayed dose of Ad26.COVS2.S
- 6E - Evaluates BNT162b2 EUA vaccination series followed by a heterologous platform delayed dose of Ad26.COVS2.S
- 7E - Evaluates Ad26.COVS2.S EUA vaccination series followed by a heterologous platform delayed dose of BNT162b2

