If a physiologic parameter, e.g., vital signs, is outside of the protocol-specified range, then the measurement may be repeated once if, in the judgment of the participating site PI or appropriate sub-investigator, the abnormality is the result of an acute, short-term, rapidly reversible condition (e.g., stress, anxiety or "white coat syndrome") or other source of error. A physiologic parameter

may also be repeated if there is a technical problem with the measurement caused by malfunctioning, or an inappropriate measuring device (i.e., inappropriate-sized BP cuff).

A subject may be re-screened if there is a transient disease status (e.g., subject complained of a “cold or fever” and met a temporary delaying enrollment criterion of acute illness or fever), or if a protocol eligibility criterion that is not met at the initial time of screening, will be met by rescreening at a later date (e.g., a medication taken within exclusionary window at the time of first screening that would not be within exclusionary window at a later rescreen).

No subjects may be screened more than twice due to a screening failure result as defined above.

Subjects will be provided the results of abnormal clinical findings necessitating follow-up at the discretion of the participating site PI or appropriate sub-investigator. Research laboratory results will not be provided to the subject.

The screening and first vaccination procedures both can be conducted at the enrollment/baseline visit.

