5. SAMPLE SIZE CONSIDERATIONS

This is a phase 1/2, open-label, multi-site clinical trial that is not designed to test a specific hypothesis. Rather, it is intended to obtain preliminary estimates in healthy adults of the safety, reactogenicity, and immunogenicity of delayed heterologous SARS-CoV-2 vaccine dosing (boost) after receipt of EUA vaccines.

Although rare AEs are not demonstrable in a clinical study of this size, there is a good chance of observing AEs of relatively low frequency (Table 3). With approximately 50 participants in each group there is a 99.5% chance of observing at least one AE of probability 10%. Similarly, with approximately 25 participants in each of the age subgroups, there is a 92.8% chance of observing at least one AE of probability 10%. Therefore, if no AEs of a given type occur in a Cohort 1 group, one can be relatively confident that they will occur in fewer than 10% of people once the vaccine is implemented.

Due to the surge in Omicron variant cases at the time of the writing of protocol version 6.0, it is anticipated that a non-negligible proportion of vaccinated individuals may be prone to asymptomatic breakthrough infections. To allow for potential larger numbers of participants enrolled in Stage 6 (Groups 15E-17E) that would subsequentially be found to have serological evidence of prior infection, the sample size is expanded to N=60/group (approximately 1:1 age strata) for these groups.

The precision with which the geometric mean titer (GMT) can be estimated from observed data depends on the standard deviation (SD) of the measurements, on the logarithmic scale, and the sample size. Table 4 displays two-sided 95% confidence intervals for the GMT for several values of the observed antibody titer assuming up to 10% attrition.

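### Rollover to 15E removes Group 4E participants without known infection while mITT keeps the infected and outside-boosted, so late 4E mITT titres tend to be biased upward, by an amount the documents cannot fix

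*SAP*

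**What the plan says.** Protocol 4.1 states that Group 4E participants still active in the study "will be offered the opportunity to roll into Group 15E, if eligible". SAP 4.1 repeats the offer and adds the data rule: "Data collected on these participants after their enrollment in Group 15E will not be included in Group 4E analyses".

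Eligibility for 15E follows the Cohort 1 criteria in the Protocol synopsis. One exclusion is "Known history of SARS-CoV-2 infection (for Cohort 1 and the primary series of Cohort 2". The inclusion criterion asks for "one or two doses of Ad26.COVS.2 at least 12 weeks prior to enrollment (Cohort 1 only". Protocol 4.1 describes 15E as people with one or two Ad26.COV2.S doses, and gives as the reason for rollover that such people without other vaccines are scarce. Protocol 5 and SAP 4.3 allow no exemptions from the criteria.

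On the analysis side:
- SAP 6.3.2 defines mITT with no exclusion for infection or outside vaccine.
- SAP 6.5 uses complete cases without imputation.
- SAP 8.1 presents immunogenicity for mITT through Day 366 and makes the per-protocol (PP) analysis optional, conditional on protocol deviations that may affect the results.
- SAP 6.3.4 removes breakthrough infection (self-reported or N-antibody positive) and non-study COVID-19 vaccine from the PP immunogenicity analysis, but says these criteria are not strictly protocol deviations.

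**The concern.** Leaving 4E depends on infection and vaccination history, and both drive late antibody levels. People known to be infected cannot move. People with an outside booster fall outside the description of 15E. The rest can move, and when they do their late samples disappear from 4E. The complete-case mITT set at late visits then holds a growing share of people whose titres reflect more than the Ad26 boost.

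Infection and outside vaccination also raise late mITT titres in 5E and 6E, but nothing there selectively removes the unaffected. Group 4E is labelled the homologous control, so a reader will naturally set its late curve beside the other two. Because the trial estimates and does not test, these estimates are its product.

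**Working it through.** **1. The plan's own precision figures.** SAP Table 4 follows GMT × exp(± t(0.975, n−1) × SD/√n), with SD on the log_e scale. All 56 cells reproduce. For GMT 100 and SD 1.0, n = 45 gives 74.0 to 135.0 and n = 22 gives 64.2 to 155.8, as printed.

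The 10%-attrition columns allow a loss of 50 − 45 = 5 per group and 25 − 22 = 3 per age stratum. Beyond that the interval widens slowly: n = 44 gives 73.8 to 135.5; n = 40, 72.6 to 137.7; n = 30, 68.8 to 145.3; n = 20, 62.6 to 159.7.

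**2. Which visits can be affected.** The 4E boost is on Day 1 and 15E entry needs at least 12 weeks (84 days) since the last Ad26 dose, so the earliest rollover is about Day 85. Days 15 and 29 are out of reach. Days 91, 181, 273 and 366 can be affected, but only for samples after a given person's rollover.

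**3. Size of the enrichment.** None of these inputs is in the documents; all are assumptions. Start from 45 active participants. Let p be the share affected (infected or outside-boosted) and unable to move, r the share of the others who move, and R the titre ratio of affected to unaffected.

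- Share affected among those left: p′ = p / [p + (1−p)(1−r)]
- Number left: n = 45 × [p + (1−p)(1−r)]
- GM factor, against the same 45 with nobody removed: R^(p′−p)

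Example, p = 0.2, r = 0.5, R = 4: p′ = 0.2/(0.2 + 0.4) = 0.333; n = 45 × 0.6 = 27; factor = 4^0.133 = 1.20.

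| r | p = 0.2: n, share, factor | p = 0.3: n, share, factor | p = 0.4: n, share, factor |
|---|---|---|---|
| 0.10 | 41, 22%, 1.02 | 42, 32%, 1.03 | 42, 43%, 1.04 |
| 0.25 | 36, 25%, 1.07 | 37, 36%, 1.09 | 38, 47%, 1.10 |
| 0.50 | 27, 33%, 1.20 | 29, 46%, 1.25 | 32, 57%, 1.27 |
| 0.75 | 18, 50%, 1.52 | 21, 63%, 1.58 | 25, 73%, 1.57 |

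With R = 10 and p = 0.3 the factors are 1.05, 1.16, 1.45 and 2.15.

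**4. Two things that shrink it.**

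*Undetected infection.* If a share u of the affected do not know and move at the same rate r, then p′ = p(1−ur) / [p(1−ur) + (1−p)(1−r)]. At r = 0.5, u = 0.5, R = 4: for p = 0.2, p′ = 0.15/0.55 = 0.273 and the factor is 1.11; for p = 0.4, p′ = 0.30/0.60 = 0.50 and the factor is 1.15. At u = 1 the factor is 1.00.

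*Infection after rollover.* Eligibility is judged when the person moves. Suppose half of p = 0.3 arises later, at equal risk in those who stay. At r = 0.5 the share is (0.15 + 0.075)/(0.15 + 0.425) = 0.39, and the factor is 4^0.091 = 1.13 (1.23 at R = 10).

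**5. Whether the PP analysis must run.** SAP 8.1 ties it to protocol deviations. SAP 6.3.4 places infection and outside vaccine outside that term. Nothing in the text therefore obliges the analysis that would remove the enrichment.

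**The case against.** The best reply is that the plan already holds the answer. The PP rules remove infection and non-study vaccine in all three groups, PP table shells exist for every assay, Table 48 shows N-antibody status by visit, and Table 49 shows positive tests and outside boosts by interval. The shells print n and the 95% CI at each visit. The groups are not randomised and the SAP specifies no contrast between them. Ending 4E follow-up at the NVX-CoV2373 dose is sensible in itself. All of this stands, and it keeps the fix small. It does not close the gap: the PP analysis is optional, and neither Table 7 nor Table 8 has a row for rollover, so a reader would see late n fall in 4E without learning why.

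Three stronger readings are tempting and not supported:

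- *Only infection-free people leave 4E.* The criterion is known history. The SAP enlarges 15E–17E because it expects enrollees "that would subsequentially be found to have serological evidence of prior infection", and Protocol 8.1.1 says "Research laboratory results will not be provided to the subject". Undetected infections can move too, which weakens the bias.
- *A written rule bars outside-boosted people from 15E.* No such exclusion is stated for Cohort 1; it is inferred from how 15E is described.
- *4E will miss the precision in Table 4.* That table is illustrative, described as covering "several values of the observed antibody titer assuming up to 10% attrition". No rollover count is given, the stated interval is exceeded only if total loss passes 5 of 50 (3 of 25 per stratum), and the first few extra losses hardly matter.

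**Conclusion.** The mechanism is in the documents and its direction is clear: at visits after rollover, 4E mITT GM, GMFR and 4-fold rates tend to be too high as measures of Ad26-boost durability, with no matching exit in 5E or 6E. This assumes that affected people have higher late titres and that at least some infections are known when rollover is offered. Protocol 8.1.3 supports the second assumption, since COVID-compatible symptoms lead to an illness visit with a locally processed swab.

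The size cannot be established. With 4-fold titres, the GM factor is near 1.0 if few people move or most infection is undetected, about 1.1 to 1.25 at 50% rollover, and about 1.5 at 75%. The tabulated values are upper readings for their inputs because they ignore undetected and later infection. Days 15 and 29 are not in question. A firmer, better-labelled late-visit analysis is warranted; replacing mITT is not.

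**What to change.** In SAP 8.1, replace the optional PP wording with a required analysis for 4E, 5E and 6E at each visit from Day 91 on. It should censor reported or N-antibody-positive infection, non-study COVID-19 vaccine and rollover to 15E in the same way, using the existing SAP 6.3.4 rules. Report it beside mITT, and use it to qualify any statement about late 4E durability drawn from mITT.

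Add the cumulative number rolled over to 15E by visit to the 4E columns of the immunogenicity tables, and a rollover row to the disposition table (Table 7).

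The cost is SAP wording and a few count rows, since infection, outside-vaccine and N-antibody results are already planned for tabulation. The statistical price is a smaller late n in every group. The censored analysis also conditions on events after baseline and so carries its own selection, which is why mITT should stay alongside it.
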